Cover Page

Official Title: Effects of Clobazam on sleep and daytime function in patients with epilepsy

NCT #: NCT02911025

Version date of document: 10/19/2020

Effects of Clobazam on sleep and daytime function in patients with epilepsy

Principal investigator: [name].

Co-investigator: [name].

Study staff: research coordinator

Consultants: BWH neuroscience institute statistical services

Background/Rationale

Many studies indicate that patients with epilepsy frequently have fragmented sleep, as well as excessive daytime somnolence (Holoway et al 2011, Meyer et al 2011, Manni et al 2010, Krishnan et al 2012). Causes include primary sleep fragmenting disorders (sleep apnea, movement disorders), nocturnal seizures that contribute to sleep fragmentation, and other abnormalities. Sleep complaints are widely reported among patients with various epilepsy syndromes (Lopez et al 2013). Insomnia is a particularly frequent complaint, seen in 40-51% of epilepsy patients (Vendrame 2013, Lopez et al 2013). Furthermore, epilepsy patients who have insomnia also have a higher frequency of depressive symptoms, as well as poorer quality of life (Vendrame 2013). Insufficient or poor quality sleep increases the risk of a variety of disorders, leading to abnormalities of endocrine (Buxton, Pavlova et al 2010) and immune function (Lange et al 2011). Insomnia probably has the some of the same consequences as insufficient sleep from other causes. For example, in a recent study in our group (Buxton, Pavlova et al, 2011), we found that sleep fragmentation, as measured by wake after sleep onset (WASO), predicts diabetes risk in insomnia patients.

Antiepileptic treatment may affect sleep (Bazil et al 2008). Effects vary by type of medication and comorbidities. Generally, with improvement of seizure control, the regularity of the sleep cycle improves and sleep becomes more consolidated. However, some antiepileptic medications have been associated with insomnia (Bazil et al 2008). Although sleep has been studied in relation to some antiepileptic medications (Bazil et al 2008, 2012, Zou et al 2012), there are no currently available published systematic reports on the effect of Clobazam on sleep. We propose to study the effect of Clobazam on sleep and daytime alertness.

Hypothesis

Primary hypothesis: Patients with epilepsy have longer, more consolidated sleep after treatment with clobazam is started. This hypothesis will be tested in a prospective study, using within subject comparisons, where by sleep measures before treatment are compared to those after treatment.

Secondary hypothesis: Sleep improvement will lead to a lesser subjective daytime sleepiness and improved quality of life. This hypothesis will be tested by comparing subjective measures of sleepiness and quality of life, measured by standard instruments (Epworth sleepiness scale score, ESS, Karolinska sleepiness scale KSS, and quality of life in epilepsy, QOLIE) relative to total sleep time and wake after sleep onset.

Methods

[figure not shown]
Research methods

Subject Population. We propose to prospectively include patients from our epilepsy clinics and inpatient who are starting treatment with Clobazam. All patients who are considered for treatment with clobazam will be approached for participation. We will exclude patients with known untreated moderate or severe sleep apnea, or with major circadian rhythm disorders, as these may confound our analyses.

Pre-treatment sleep symptoms will be evaluated using validated instruments including, Pittsburgh Sleep Quality Inventory (PSQI), depression symptoms - Beck Depression Inventory (BDI), and severity of insomnia - Insomnia Severity Index (ISI). We will also record the subject's Body Mass Index (BMI). Subjects will then be asked to complete a one week sleep and seizure log, simultaneous wrist actigraphy monitoring, and daytime sleepiness Epworth Sleepiness Scale (ESS), and daily visual analog scale (Karolinska sleepiness scale, KSS), as well as quality of life (QOLIE), prior to starting treatment – **baseline phase**.

Treatment with Clobazam, as well as clinical follow-up will be performed as per standard of care. After the effective dose is reached and the treating physician confirms that the medication is well tolerated, subjects will repeat the same log, actigraphy and questionnaire measurements over a one week period– **treatment phase**. We will then compare total sleep time (TST), wake after sleep onset (WASO), subjective sleep (from sleep log), and sleepiness prior to treatment to the same measures after treatment with Clobazam (Fig. 1).

Fig 1: Study schema

Statistical analyses

Primary analyses will include within subject comparison of total sleep time (TST) and wake after sleep onset (WASO), as measured by actigraphy, before versus after treatment. Preliminary analysis indicate that 20 subjects will give us 98% power to demonstrate efficacy of Clobazam to improve the above sleep measures with effect size of 3, assuming the standard deviation is 3 with a two-sided one group t-test at $\alpha=0.05$ level.

Our secondary hypothesis is that in epilepsy patients, quality of life and subjective sleepiness improve with improved sleep. To test this hypothesis, we will correlate the rate of sleepiness with the sleep variable. The dependant variables will be ESS, KSS (subjective

sleepiness measures), and the independent variables will be WASO and TST. Bonferoni correction will be performed to adjust for multiple comparisons.

The Neuroscience Institute at the Brigham and Women's Hospital provides statistical analyses at a reduced rate to neurologists within our department.

Timeline

Within three months of the start of the funding period, we plan to have recruited study staff, purchased equipment and obtained Human Subject's Committee approval. At this time, recruitment of eligible patients will start. Testing of each subject requires approximately two month of monitoring: one week of actigraphy sensor monitoring before treatment (baseline phase), subject's titration period as dictated by their treating physician, and another 1 week after the prescribed dose has been reached - treatment phase. These two testing phases will be approximately a month apart to ensure that the enrolled patients have reached effective dose and have not reported serious side effects. We will aim to have two subjects enrolled and actigraphy data collection done simultaneously. Thus, with efficient recruitment and minimal attrition rate, 20 participants can complete the study within 18 months of the start of the funding period. Proposed timeline would be as follows:

Study start: September 2014

First subject enrolled: December 2014

Completion of enrollment: May 2016

Final study report: June 2016

Challenges and plans to address them

- 1) **Adverse events to Clobazam.** It is possible that the patients enrolled in the study experience adverse effects of Clobazam or for other reasons need to change the medication. In these cases, we may need to exclude these participants. In this case, the overall number of enrolled participants will need to be adjusted to allow adequate analyses.
- 2) **Interactions with other medications and medication changes.** The patients who are eligible for the study may be on other medications. Some may need medication change during the data acquisition. In these cases, treatment will follow standard clinical care guidelines (to avoid any adverse medical outcomes). Any medication changes will be recorded for post-hoc analyses.
- 3) **Recruitment.** We aim to approach all eligible patients from our clinic and inpatient for participation. However, it is possible that too few will volunteer to participate. In this case, advertisement will be broadened and neurologists and epileptologists from around the Greater Boston approached for recruitment of eligible patients. As more than 1000 patients are seen by epileptologists within our division, and we have successfully recruited patients for other studies on sleep and epilepsy (Pavlova et al, 2013), we anticipate little difficulties.

Alternate analyses if challenges cannot be addressed

In case our study is under-powered to detect a statistically significant difference in the primary outcome measures, more detailed analyses will be performed on the secondary outcome measures – the subjective improvement of sleepiness or of depressive symptoms, as well as overall quality of life.

Publication plans

Meetings/Congresses

We will aim to submit an abstract to the major annual academy meetings – American Epilepsy Society and American Academy of Neurology. A more detailed sleep analysis may additionally be presented to the American academy of sleep medicine.

Scientific/Medical Journals

We will prepare a manuscript from the acquired results and submit for publication to the journal *Epilepsia* (a major journal for research on epilepsy). An alternative journal may be *Epilepsy Research* or *Epilepsy and Behavior*.

Study impact

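### The seizure log kept in both weeks enters no analysis, so the causal secondary hypothesis is open to confounding by seizure change and the primary sleep change is reported without seizure context

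*Combined protocol and SAP*

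**What the plan says.** All references are to the combined protocol and SAP.

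- **Background/Rationale.** Among the causes of poor sleep in epilepsy it lists "nocturnal seizures that contribute to sleep fragmentation". It then says: "Generally, with improvement of seizure control, the regularity of the sleep cycle improves and sleep becomes more consolidated". The following sentence notes that some antiepileptic drugs are linked to insomnia.
- **Hypothesis.** The primary hypothesis is that sleep is longer and less broken once clobazam has been started; no route is specified. The secondary hypothesis is causal in form: "Sleep improvement will lead to a lesser subjective daytime sleepiness and improved quality of life". Sleepiness and quality of life are to be compared relative to TST and WASO.
- **Research methods.** For the baseline phase, "Subjects will then be asked to complete a one week sleep and seizure log", with wrist actigraphy over the same week. The same log and measurements are repeated for one week on treatment, once an effective dose has been reached and tolerability confirmed. The quantities listed for comparison are TST, WASO, subjective sleep from the log, and sleepiness.
- **Statistical analyses.** The primary analysis is a "within subject comparison of total sleep time (TST) and wake after sleep onset (WASO), as measured by actigraphy, before versus after treatment". The secondary analysis takes ESS and KSS as dependent variables and WASO and TST as independent variables, with a Bonferroni correction.
- **Challenges and plans to address them; Alternate analyses.** Medication changes are kept for post-hoc analysis. The fallback outcomes are sleepiness, depressive symptoms and quality of life.

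Nowhere do seizure counts or seizure nights appear as an outcome, a covariate, a stratifier or a rule for including nights. There is no control group.

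**The concern.** The plan names seizures as a cause of the outcome it measures, collects data on them in both weeks, and then leaves those data unused. Two things are lost.

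First, sleep is compared between two single weeks. If TST or WASO changes, the planned output will not show whether the number of seizure nights changed as well. Without a control group, a chance difference in seizures between the two weeks would look the same as a treatment-related one.

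Second, and more seriously, the secondary hypothesis says that better sleep leads to better daytime function, but it is tested by a correlation with no seizure term. If fewer seizures improve sleep and also improve sleepiness or quality of life by a route other than sleep, the two sides will move together even where sleep has no effect on daytime function. The correlation would then be read as support for a causal statement that it does not test.

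**Working it through.** **1. The plan's own figure.** The Statistical analyses section states that "20 subjects will give us 98% power to demonstrate efficacy of Clobazam to improve the above sleep measures". The inputs given there are a difference of 3 and an SD of 3 (neither with a unit), tested by a one-sample t-test at a two-sided alpha of 0.05. With n = 20:

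- noncentrality = √20 × 3/3 = 4.47, with 19 degrees of freedom;
- power from the noncentral t distribution = 98.9%.

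The stated 98% is reproduced. It is power for the total before-after change and is the same whatever share of that change runs through seizures.

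**2. How far seizure nights could move the primary measure.** Assume the weekly value is the mean of 7 nights, a seizure night changes the measure by X units, and a patient has k fewer seizure nights in the treatment week. The shift in the weekly mean is kX/7.

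| k | X | kX/7 |
|---|---|---|
| 0 | any | 0 |
| 1 | 10 | 1.4 |
| 1 | 15 | 2.1 |
| 1 | 30 | 4.3 |
| 2 | 30 | 8.6 |

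Neither k nor X is in the document, and the planned difference of 3 has no unit, so this table shows only how the shift depends on its inputs. A value of X can always be found that returns exactly 3 (for k = 1, X = 3 × 7 = 21), so such a match is not evidence of size.

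**3. Correlation induced in the secondary test.** Suppose sleep has no effect on daytime function, and seizure change correlates a with sleep change and b with change in daytime function. The induced correlation is then a × b:

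- a = b = 0.4: 0.4 × 0.4 = 0.16;
- a = b = 0.6: 0.6 × 0.6 = 0.36;
- a = 0 or b = 0: 0.

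The values of a and b are assumptions. The formula is written for change scores; the plan does not say whether change scores or raw scores will be correlated. With raw scores the same argument applies to differences in seizure count between patients.

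**4. What a seizure-free-night analysis could show at n = 20.** If a share s of the planned difference runs through seizures, the remainder is 3(1 − s). With SD 3 and all 20 patients retained:

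| s | Remaining difference | Power |
|---|---|---|
| 0% | 3.00 | 98.9% |
| 25% | 2.25 | 88.9% |
| 50% | 1.50 | 56.5% |
| 75% | 0.75 | 18.6% |
| 100% | 0 | 5% (alpha) |

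A real effect outside seizure control would often be missed once half or more of the change runs through seizures. Losing nights or patients would not help.

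**The case against.** The strongest objection is that seizure reduction caused by clobazam is a mediator, not a rival explanation. The primary hypothesis concerns sleep after the drug is started and claims no effect independent of seizure control. If clobazam reduces seizures and sleep improves as a result, that is an effect of clobazam on sleep. This stands in full. A reader might infer that the primary comparison is invalid, or that a positive result could not be credited to clobazam because fewer seizures might explain it. The document does not support that reading: the test answers the total-change question it poses.

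It is also fair to say that the Background/Rationale speaks of what happens *generally*, and does not say that every effective drug consolidates sleep. Nor does it define an effective dose, so fewer seizures in the treatment week is an inference. The size figures rest on assumed inputs. An analysis limited to seizure-free nights conditions on something that happens after treatment starts, compares different mixes of nights and patients, and in an uncontrolled study cannot rule out time or regression to the mean. It cannot carry a decision rule.

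The objection does not reach the secondary hypothesis. There seizure change is a possible common cause of both variables, and the mediator argument gives no protection. Nor does it cover chance differences in seizures between the two weeks, which are not a drug effect.

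**Conclusion.** The point holds as a gap in the analysis, not as a flaw in the primary test. The seizure log is collected in both weeks and used nowhere. As a result, the primary change cannot be set against any change in seizure nights, and the causal secondary hypothesis rests on an unadjusted correlation that seizure change can confound.

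The size is unknown. The document gives no seizure frequency, no sleep loss per seizure night and no unit for the planned difference, and any shift is zero for a patient with no seizure nights in either week. A reader might infer from the arithmetic that one fewer seizure night could account for the whole planned effect. That follows only for a chosen value of X, which nothing in the document supports. The induced correlation of 0.16 to 0.36 likewise depends on assumed correlations of 0.4 to 0.6.

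The secondary point assumes that seizures affect daytime function partly by a route other than sleep. That is plausible, but the document does not state it.

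**What to change.** Keep the primary test as it is. In the Statistical analyses section, add three items:

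1. **Secondary associations.** Include logged seizure count (its change, if change scores are used) as a covariate in the sleep-to-sleepiness and sleep-to-quality-of-life associations, and report the adjusted result beside the unadjusted one. State at the same time whether raw or change scores are analysed.
2. **Seizure context.** Report logged seizure nights in the baseline and treatment weeks next to the TST and WASO changes. This shows whether the weeks differed in seizures, but not why.
3. **Exploratory repeat.** Repeat the TST and WASO comparison on nights without a logged seizure, labelled supportive and exploratory. Do not make any claim depend on it. If the change is not seen on those nights, describe it as *not separated from seizure control*, not as evidence that there is no other effect.

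The cost is mainly analysis wording, since the log is already collected; items 2 and 3 need its entries to be assignable to nights. The covariate uses one degree of freedom at n = 20, and item 3 loses some nights, mostly in patients with frequent seizures. Separation will be incomplete because logs miss unnoticed seizures.

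### Both primary outcomes come from actigraphy, but the plan neither hides the phase during processing nor fixes how sleep intervals are set and nights excluded

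*Combined protocol and SAP*

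**What the plan says.** The Hypothesis section states a direction: "Patients with epilepsy have longer, more consolidated sleep after treatment with clobazam is started". It tests this in a single group, "using within subject comparisons, where by sleep measures before treatment are compared to those after treatment".

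Under Research methods, treatment is ordinary clinical care: "Treatment with Clobazam, as well as clinical follow-up will be performed as per standard of care". Before treatment, subjects "complete a one week sleep and seizure log, simultaneous wrist actigraphy monitoring" and fill in questionnaires. The second week starts on a clinical judgement: "After the effective dose is reached and the treating physician confirms that the medication is well tolerated". The baseline assessments are then taken again in full: "subjects will repeat the same log, actigraphy and questionnaire measurements over a one week period".

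Statistical analyses makes TST and WASO the primary measures, "as measured by actigraphy, before versus after treatment". It bases 20 subjects on a difference of 3, an SD of 3 and a two-sided one-group t-test at 0.05, with stated power of 98%.

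The cover page lists two investigators, a research coordinator and a consulting statistical service. The document says nothing on masking of subjects, staff, scorer or analyst. It gives no device, scoring algorithm, interval rule, night-exclusion rule, scorer or coding of files by phase. The study schema (Fig. 1) was not available in the text reviewed, so it could not be checked for any of this.

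**The concern.** Patients and treating physicians know which week is which, and there is no comparator. The sleep log, the sleepiness scales and the quality-of-life instrument are self-reports by patients who know they are treated. In the primary outcomes, by contrast, the reading of the recording can be shielded from expectation at little cost, and the plan does not use that protection.

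TST and WASO depend on where each sleep interval begins and ends and on which nights count. The plan leaves both open. If someone decides them by eye while knowing the phase, the decisions may lean toward longer and less broken sleep in the treated week. A paired analysis removes stable differences between patients. It does not remove a processing difference that follows phase, because that difference is part of the before/after contrast being tested.

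At stake is whether a significant change in TST or WASO can be read as a change in the recorded sleep rather than, in part, in how the recordings were handled.

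**Working it through.** **Inputs from Statistical analyses:** n = 20, difference 3, SD 3 (units not given), two-sided one-group t-test, alpha 0.05. The SD is taken as that of the within-patient differences, as a one-group test requires.

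**1. Reproduce the stated power.**
- Degrees of freedom = 20 − 1 = 19; two-sided 5% critical value = 2.093.
- Standard error = 3/√20 = 0.671.
- Noncentrality = 3/0.671 = 4.47.
- Power from the noncentral t = 98.9%, against 98% stated. The figure reproduces to within one point, so these inputs can be used below.

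**2. Illustrate a processing shift with no true effect.** Let b be an assumed mean difference between weeks that arises only from processing, in the direction of the hypothesis. The chance of a false significant improvement is P(T > 2.093), where T is noncentral t with 19 df and noncentrality b/0.671.

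| Assumed mean shift b | Share of planned effect (b/3) | Noncentrality | Chance of false significant improvement |
|---|---|---|---|
| 0 | 0% | 0 | 2.5% |
| 0.25 | 8% | 0.37 | 5.4% |
| 0.5 | 17% | 0.75 | 10.5% |
| 1.0 | 33% | 1.49 | 29.3% |

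The last column counts only results in the hypothesised direction, so its baseline is half of 5%. It applies to one outcome at a time at the 0.05 level.

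**3. What the table does and does not show.** The values of b are assumptions; nothing in the document supports any of them. Because the 3 and the SD of 3 have no units, b cannot be turned into minutes of sleep and judged for plausibility. The table shows how sensitive a 20-patient paired test is to a small consistent shift. It does not estimate the bias in this study.

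**4. Effect of the remedy on the design.** Masked processing changes neither n, the SD nor the test, so the power in step 1 stands.

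**The case against.** The strongest reply is that actigraphy is a device measure and the document describes no manual step. Research methods treats subjective sleep from the log as a separate comparison, not as an input to the actigraphy values. With fully automatic interval setting and no discretionary exclusions, scorer bias would be close to zero. This stands, and it is why the point is conditional. It does not remove the point, because the document does not say that scoring is automatic.

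A reader might infer several stronger things that the text does not support:

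- **That scoring will be unmasked, or done week by week with phase-labelled logs.** The document gives no scoring time and no labelling. The comparison is described only after both phases, which fits batch processing equally well. Absence of masking is inferred from the design and from silence; the term open-label is not used either.
- **That the staff who collect the data also make the comparison.** A statistical service is named as consultant. That is not masking, but it does not show that one team does everything.
- **That every patient is shifted the same way.** Nothing shows this, and an average shift is enough to bias the test. Nor need one habit favour both outcomes: widening a sleep interval can raise TST and also add wake time to WASO, which works against the hypothesis on WASO.

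It is also fair to say that a fixed automatic rule would remove most of the discretion without any coding, and that larger threats remain. The first is accepted: the rule belongs in the fix, with masking protecting whatever judgement is left. The second is true, but does not excuse leaving a cheap safeguard unused. Finally, with about two patients monitored at a time (Timeline) and an investigator as scorer, masking could be imperfect. Removing dates and scoring both weeks together reduces that weakness without abolishing it.

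**Conclusion.** The concern holds in a limited form. Processing the recordings with knowledge of the phase would comply with the plan as written, and the steps that turn a recording into TST and WASO are not fixed in advance. Any judgement in those steps could move both primary outcomes on average toward the hypothesis, and the analysis could not detect it.

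The size is unknown. The illustration rests on the plan's n and SD, no true effect, and shifts chosen for illustration. On those terms, a shift of one-sixth of the planned effect roughly quadruples the chance of a false improvement (10.5/2.5 = 4.2). The document does not support a claim that the results will be biased, or by how much.

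This is a worthwhile, inexpensive improvement rather than a fatal flaw. Masked processing would leave untouched the lack of a control group, regression to the mean, and patients changing their sleep behaviour because they know they are treated.

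**What to change.** Add to Statistical analyses:

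1. Name the scoring algorithm, the rule for setting sleep intervals and the rule for excluding nights before any recording is scored. If interval setting is fully automatic, say so.
2. When a patient's second week is in, the coordinator removes dates and phase labels from both recordings and from the matching bed-time and rise-time entries, gives each a random code, and holds the key.
3. One existing investigator sets intervals and excludes nights for both weeks in one session, using the same prespecified algorithm and rule.
4. TST and WASO are locked before the code is opened.

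The cost is a coding step for about 40 recordings (20 patients × 2 weeks), and scoring of the first week waits until the second is complete. No extra staff, visits, procedures or patients are needed, and sample size and power do not change. Recordings already collected could be coded and scored in the same way from the stored files.

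### Holm's step-down could replace Bonferroni for the secondary sleepiness–sleep correlations: same family-wise error control, never less power, and a useful gain only if several associations are real

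*Combined protocol and SAP*

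**What the plan says.** In the combined protocol and SAP, the section Statistical analyses says of the secondary hypothesis that "we will correlate the rate of sleepiness with the sleep variable". ESS and KSS are the dependent variables, "and the independent variables will be WASO and TST". Two outcomes by two predictors make four correlations. The paragraph ends: "Bonferoni correction will be performed to adjust for multiple comparisons". No step-down version is mentioned, and neither the number of tests in the family nor its significance level is stated.

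The Hypothesis section is wider. It lists the subjective measures as ESS, "Karolinska sleepiness scale KSS, and quality of life in epilepsy, QOLIE) relative to total sleep time and wake after sleep onset". If QOLIE is analysed in the same way, there are six correlations.

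The only power statement is for the primary before–after comparison: "20 subjects will give us 98% power to demonstrate efficacy of Clobazam", with an "effect size of 3, assuming the standard deviation is 3". No power is claimed for the correlations.

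**The concern.** Bonferroni holds every test to 0.05/m, whatever the other tests show. Holm starts at the same threshold and relaxes it after each rejection, with no loss of family-wise control. Choosing Bonferroni therefore gives up some power and buys no extra protection.

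The situation in which Holm helps is plausible here. The secondary hypothesis is broad, and it is examined with two scales of sleepiness against two measures from one actigraphy record. If it is true, more than one association may well be real. The sample is small, the section on challenges allows for exclusions after adverse effects or medication changes, and the section on alternate analyses gives the secondary outcomes more weight if the primary comparison proves under-powered. What is at stake is how many of the secondary associations can be declared, not whether the error rate is controlled.

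**Working it through.** **1. The plan's own figure.** Inputs from Statistical analyses: n = 20, effect 3, SD 3, two-sided one-group t-test, α = 0.05. Noncentrality = √20 × 3/3 = 4.47 with 19 degrees of freedom. The noncentral t distribution gives power of 98.9%, against 98% stated, so the figure is reproduced to within a point. It concerns the primary comparison only and does not depend on the choice between Bonferroni and Holm.

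**2. Thresholds for four correlations.** Inputs: m = 4 (ESS and KSS, each with WASO and TST), n = 20, family-wise two-sided 0.05 (assumed, because the plan states no level for this family). The critical correlation is |r| = t/√(t² + 18), where t is the two-sided critical value on 18 degrees of freedom.

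| Ordered p-value | Bonferroni | Holm | Critical \|r\| under Holm |
|---|---|---|---|
| smallest | 0.0125 | 0.05/4 = 0.0125 | 0.547 |
| second | 0.0125 | 0.05/3 = 0.0167 | 0.528 |
| third | 0.0125 | 0.05/2 = 0.025 | 0.499 |
| largest | 0.0125 | 0.05/1 = 0.05 | 0.444 |

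Under Bonferroni the critical |r| is 0.547 throughout. Holm stops at the first p-value that exceeds its threshold. The two first steps are identical, so the chance of at least one rejection must be identical too.

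**3. Size of the gain, by simulation.** Multivariate normal data, n = 20, Pearson tests. All correlations are assumptions. The main setting has WASO–TST −0.6 and ESS–KSS 0.6, with all four sleep–sleepiness associations real and equal in size.

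| True \|r\|, all four real | Average power, Bonferroni | Average power, Holm |
|---|---|---|
| 0.3 | 11% | 13% |
| 0.5 | 41% | 50% |
| 0.6 | 66% | 76% |

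- At |r| = 0.5 the chance of at least one significant correlation is about 75% with either method.
- With no real association, family-wise error is about 4.2% with either method.
- With a within-pair correlation of 0.5 the averages are nearly the same: 41.4% to 49.8% at |r| = 0.5, and 65.6% to 76.0% at 0.6.

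**4. Fewer real associations** (within-pair correlation 0.5):

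| Real associations | True \|r\| | Bonferroni | Holm | Gain (points) |
|---|---|---|---|---|
| two | 0.3 | 10.8% | 11.3% | 0.5 |
| two | 0.5 | 41.6% | 43.7% | 2.1 |
| two | 0.6 | 65.5% | 68.2% | 2.7 |
| one | 0.5 | 41.5% | 41.6% | 0.1 |

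**5. Six tests (QOLIE added).** With all six real at |r| = 0.6 and within-pair correlation 0.6, average power rises from 60% to 71%.

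**The case against.** The strongest reply is that nothing here is wrong. Bonferroni is valid, prespecified and conservative, it conflicts with no other statement in the documents, and no power was promised for these correlations. That stands: the point is about efficiency only.

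A reader might infer that real associations would be missed because of Bonferroni. The documents do not support that. They give no correlations, and Holm cannot improve the chance that any correlation at all reaches significance. It adds rejections only after one test has passed 0.0125. The most that can be said is that some could be missed when several are real.

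A reader might also be drawn to the chance of detecting all four associations, which at |r| = 0.5 rises from about 12% to 29%. The plan does not require every correlation to be significant for the secondary hypothesis to be supported, so this is not the measure of benefit. Nor do the documents say how closely WASO tracks TST or ESS tracks KSS. If the measures are close to duplicates, extra rejections add little information.

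The small sample is the larger limit. With all four at |r| = 0.3, even unadjusted tests have only about 25% power, against 11% with Bonferroni and 13% with Holm.

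Two practical objections also stand. Naming Holm alone would leave the family undefined. And the document is dated October 2020 while its Timeline planned a final report for June 2016; it does not show whether outcome data had been seen. A move to a less conservative rule after seeing them would be a post hoc change.

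**Conclusion.** The point holds as a suggestion for improvement. Holm gives the same family-wise control as the planned Bonferroni correction under any dependence and is never less powerful. Under the assumed correlations the gain in average power per test is about 2 points at |r| = 0.3 and 9 to 10 points at 0.5 to 0.6 if all four associations are real. It is 0.5 to 3 points if two are real and about 0.1 point if only one is. The chance of at least one significant result is unchanged in every case.

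The dominance of Holm over Bonferroni needs no assumption about the data. The sizes rest on 20 analysed patients, normal data, Pearson tests, a family of four at two-sided 0.05, and correlations that the documents do not supply.

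**What to change.** Before the outcome data are analysed, replace the Bonferroni sentence in Statistical analyses with:

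> P-values of the four secondary correlations (ESS and KSS, each with WASO and TST; six if QOLIE is included) will be adjusted by Holm's step-down procedure at family-wise two-sided 0.05.

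The authors should decide whether QOLIE belongs to the family and keep only the matching number. They should also say whether the existing sentence was meant to cover the two primary comparisons, since the replacement applies to the secondary correlations only.

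The cost is one sentence. There is no loss of error control and no change to sample size or data collection. The one inconvenience is that simultaneous confidence intervals that match Holm's decisions are less simple than Bonferroni intervals. If the outcome data have already been examined, keep Bonferroni as the planned analysis and label any Holm results as post hoc.
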